12.4.2. Treatment Emergent Flag for Adverse Events

Flag	Definition
Treatment Emergent	If AE onset or worsening date is on or after treatment start date & on or before treatment stop date plus 30 days.

NOTES:

- If the study treatment stop date is missing, then the AE will be considered to be On-Treatment.

12.5. Appendix 5: Data Display Standards & Handling Conventions

12.5.1. Reporting Process

Software	

 The currently supported versions of SAS software will be used. 	
Reporting Area	
HARP Server	: US1SALX00259
HARP Compound	: Compound: GSK2816126, Study:117208
Analysis Datasets	

 Analysis datasets will be created according to Legacy GSK Analysis and Reporting (A&R) dataset standards 	
Generation of RTF Files	

 RTF files will be generated for SAC. 	

12.5.2. Reporting Standards

General

 The current GSK Integrated Data Standards Library (IDSL) will be applied for reporting, unless otherwise stated (IDSL Standards Location: https://spope.gsk.com/sites/IDSLLibrary/SitePages/Home.aspx): 
 4.03 to 4.23: General Principles 5.01 to 5.08: Principles Related to Data Listings 6.01 to 6.11: Principles Related to Summary Tables 7.01 to 7.13: Principles Related to Graphics
Formats

 GSK IDSL Statistical Principles (5.03 & 6.06.3) for decimal places (DP's) will be adopted for reporting of data based on the raw data collected, unless otherwise stated. Numeric data will be reported at the precision collected on the eCRF. The reported precision from non eCRF sources will follow the IDSL statistical principles but may be adjusted to a clinically interpretable number of DP's.
Planned and Actual Time

 Reporting for tables, figures and formal statistical analyses: 
 Planned time relative to dosing will be used in figures, summaries, statistical analyses and calculation of any derived parameters, unless otherwise stated. The impact of any major deviation from the planned assessment times and/or scheduled visit days on the analyses and interpretation of the results will be assessed as appropriate. Reporting for Data Listings: 
 Planned and actual time relative to study drug dosing will be shown in listings (Refer to IDSL Statistical Principle 5.05.1). Unscheduled or unplanned readings will be presented within the subject's listings. Visits outside the protocol defined time-windows (i.e. recorded as protocol deviations) will be included in listings but omitted from figures, summaries and statistical analyses.
Unscheduled Visits

 Unscheduled visits will not be included in summary tables. Unscheduled visits will be included in figures. All unscheduled visits will be included in listings.

Descriptive Summary Statistics	
Continuous Data	Refer to IDSL Statistical Principle 6.06.1
Categorical Data	N, n, frequency, %
Graphical Displays	

 Refer to IDSL Statistical Principals 7.01 to 7.13. 	

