7.3. Clinical Laboratory Analyses

Laboratory evaluations including the analyses of Chemistry laboratory tests, Haematology laboratory tests, and liver function tests will be based on GSK Core Data Standards. The details of the planned displays are in [Appendix 10: List of Data Displays](#).

The assessment of laboratory toxicities will examine the following laboratory tests:

Hematology			
Platelet Count	RBC Indices:		Automated WBC Differential:
Red Blood Cell (RBC) Count	Mean Corpuscular Volume (MCV)		Neutrophils
White Blood Cell (WBC) Count (absolute)	Mean Corpuscular Hemoglobin (MCH)		Lymphocytes
Reticulocyte Count	Mean Corpuscular Hemoglobin Concentration (MCHC)		Monocytes
Hemoglobin			Eosinophils
Hematocrit			Basophils
Clinical Chemistry			
Blood Urea Nitrogen (BUN)	Potassium	Alanine Aminotransferase (AST)	Total and direct bilirubin
Creatinine	Chloride	Aspartate Aminotransferase (ALT)	Uric Acid
Sodium	Calcium	Alkaline phosphatase	Total Protein
Magnesium	Glucose	Lactate Dehydrogenase (LDH)	
Follicle Stimulating Hormone (FSH) and estradiol (as needed in women of non-child bearing potential and all peri menopausal women)			
Pregnancy test for females (serum B-HCG at screening, Urine or serum B-HCG during Continuation Phase)			

Laboratory grades will be evaluated using CTCAE v4.0. However, some tests are not graded using CTCAE.

For hematology, Red Blood Cell (RBC) is not gradable by CTCAE v4.0.

For clinical chemistry, BUN and creatinine clearance are not gradable by CTCAE v4.0. For sodium, potassium, calcium, glucose, and magnesium there will be two bi-directional parameters (hyper and hypo) created and the tests will be graded by CTCAE v4.0 in both directions.

Separate summary tables for hematology and chemical chemistry will be produced as detailed below. Liver function and pancreatic laboratory tests will be included with chemical chemistry.

Summary of worst case toxicity grade of lab values increase from baseline grade across all scheduled visits will be generated by dose level for all the lab tests that are gradable by CTCAE v4.0. Any increase to a higher grade from baseline will be summarized. Missing baseline grade will be assumed as grade 0. For laboratory tests that are graded for both low and high values, summaries will be done separately and labeled by direction, e.g., sodium will be summarized as hyponatremia and hypernatremia.

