7.4. Other Safety Analyses

The analyses of non-laboratory safety test results including ECGs and vital signs will be based on GSK Core Data Standards, unless otherwise specified. The details of the planned displays are presented in [Appendix 10: List of Data Displays](#).

Vital Signs

Listing of vital signs including Systolic BP, diastolic BP, heart rate, body temperature, height and weight at each scheduled visit will be provided.

ECOG (Eastern Cooperative Oncology Group) Performance Status

A summary of worst case post-baseline ECOG status shift from baseline among all visits by dose level will be provided. A supporting listing including performance status and change from baseline will also be provided.

ECG

A summary of the number and percentage of subjects who had normal and abnormal ECG findings will be displayed by scheduled visits as well as for the worst case post-baseline for each dose level. A listing of abnormal ECG findings will be provided. ECG interval values will also be listed.

The mean of ECG values at each collection point will be used for ECG analyses

Summary of the worst case QTc (QTcF and QTcB) post-baseline values relative to baseline will be provided by dose level. The QTc values (QTcF and QTcB) will be

rounded to the integer and the values will be categorized into the following ranges: Grade 0 (<450), Grade 1 (450-480), Grade 2 (481-500), and Grade 3 (≥ 501).

Summary of the worst case QTc (QTcF and QTcB) increase from baseline by dose level will be provided. The categories of 'Increase of ≤ 30 msec' 'Increase of 31-60 msec' and 'Increase of > 60 msec' will be used. A summary of change in QTc value will display the number and percentage of subjects with a change within each category in the worst case post-baseline among all visits.

Baseline results are defined by the nearest timepoint prior to first dose. The baseline QTc value is determined by the mean of the triplicate Cycle 1 Day 1 (C1D1) pre-dose QTc results. If these results are not available, then the mean of QTc of the screening triplicate QTc results would be used. Subjects with a missing baseline value will be assumed to have a normal baseline value.

LVEF (Left Ventricular Ejection Fraction)

LVEF results will be listed with subject level details including absolute change from baseline. Only the post-baseline assessments that used the same method (ECHO or MUGA) as the baseline assessments will be used to derive the change from baseline.

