12.3. Appendix 3: Assessment Windows

No assessment windows will be applied.

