12.6. Appendix 6: Derived and Transformed Data

12.6.1. General

Multiple Measurements at One Analysis Time Point

Mean of the measurements will be calculated and used in any derivation of summary statistics but if listed, all data will be presented.If there are two values within a time window the value closest to the target day for that window will be used. If values are the same distance from the target, then the mean will be taken.Participants having both High and Low values for Normal Ranges at any post-baseline visit for safety parameters will be counted in both the High and Low categories of “Any visit post-baseline” row of related summary tables. This will also be applicable to relevant Potential Clinical Importance (PCI) summary tables.
Study Day

Calculated as the number of days from First Dose Date:
Ref Date = Missing → Study Day = MissingRef Date < First Dose Date → Study Day = Ref Date – First Dose DateRef Date ≥ First Dose Date → Study Day = Ref Date – (First Dose Date) + 1

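### Worst-case laboratory grade tables are limited to scheduled visits, and the general table rules have no worst-case exception, so the most severe values can be missing

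*SAP*

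**What the plan says.** Four sets of rules in the SAP bear on the worst-case safety tables.

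- **Section 12.5.2, Reporting Standards.** "Unscheduled visits will not be included in summary tables". Separately, a visit that falls outside its protocol window, and so counts as a deviation, "will be included in listings but omitted from figures, summaries and statistical analyses". Neither sentence makes an exception for worst-case or maximum displays. Unscheduled visits are kept in figures and listings.
- **Section 7.3, Clinical Laboratory Analyses** (Tables 3.8 and 3.9). "Summary of worst case toxicity grade of lab values increase from baseline grade across all scheduled visits will be generated by dose level".
- **Section 7.4, Other Safety Analyses.** The QTc increase summary (Table 3.14) counts subjects "with a change within each category in the worst case post-baseline among all visits". The ECOG shift (Table 3.15) is likewise taken over all visits.
- **Section 12.6.1, General.** Repeat readings are handled as follows: "Mean of the measurements will be calculated and used in any derivation of summary statistics", although listings show every value. If two values share a time window, the one nearest the target day is kept. Section 12.3 says "No assessment windows will be applied".

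Sections 7.3, 7.3.1 and 7.4 put no scheduled-visit limit on the hepatobiliary table (3.10), the table of laboratory tests that CTCAE does not grade (3.11) or the maximum QTc table (3.13).

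**The concern.** A worst-case table should report the most severe value each subject had. Unscheduled samples may be drawn because something looks wrong, and a late or early visit may coincide with illness. If those values are left out, the table can understate the worst value, and the loss does not average out across subjects.

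The stake is the reported safety profile. Section 2.2 places changes in safety assessments, including laboratory and cardiac parameters, among the Part 1 primary endpoints. Section 2.4 makes the Part 1 dose-escalation analysis purely descriptive, so these counts and percentages are themselves the result. Dose columns are small (Section 2.3: one subject per level in accelerated titration, then 3+3), so one subject changes a column visibly.

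There is also a reproducibility problem. For Tables 3.14 and 3.15, two programmers could follow different sections and produce different tables.

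**Working it through.** The plan gives no figure to reproduce. The check has two parts: the rules against each table, then the possible size.

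**1. Rules by table**

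| Table | Specific rule | Effect of Section 12.5.2 |
|---|---|---|
| 3.8, 3.9 laboratory grades | Scheduled visits only (7.3) | Agrees: unscheduled values explicitly out |
| 3.14 QTc increase, 3.15 ECOG shift | All visits (7.4) | Contradicts |
| 3.10 hepatobiliary, 3.11 non-gradable tests, 3.13 maximum QTc | No visit limit (7.3, 7.3.1, 7.4) | Only the general rule could exclude values; scope unstated |

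For ECG findings, Section 7.4 asks for scheduled visits and, in addition, the worst post-baseline case. It therefore treats the two as different things; Section 12.5.2 does not.

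**2. Direction.** With the baseline held fixed, the maximum over a subset cannot exceed the maximum over the full set. The mean of repeats cannot exceed the largest repeat. Each subject's reported severity can therefore only fall or stay the same.

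**3. Single-subject examples (values assumed, thresholds from the SAP)**

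- QTc bands (7.4): below 450, 450–480, 481–500, and 501 or more. Take scheduled values of 445 and 470 and an unscheduled 512. The scheduled maximum is 470, Grade 1. The maximum of all values is 512, Grade 3.
- ALT criterion (7.3.1): at least 3 × ULN. Repeats of 3.6 and 2.0 × ULN at one time point average (3.6 + 2.0) / 2 = 2.8, which misses the criterion. The larger value meets it.

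**4. Expected count.** Shown = true count × (1 − share of those worst values at excluded visits). Take N = 40, the top of the Part 1 range in Section 2.3, and an assumed true rate of 20%, so 0.20 × 40 = 8 subjects. The SAP gives no share, so a range is shown.

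| Share (assumed) | Subjects shown | Rate shown |
|---|---|---|
| 5% | 8 × 0.95 = 7.6 | 19% |
| 20% | 8 × 0.80 = 6.4 | 16% |
| 30% | 8 × 0.70 = 5.6 | 14% |
| 50% | 8 × 0.50 = 4.0 | 10% |

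**5. Chance that at least one subject is understated.** Let u be the share of all subjects whose grade is lowered by the exclusion (assumed, and independent between subjects). The chance is 1 − (1 − u)^n.

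| u | n = 3 | n = 6 | n = 30 | n = 40 |
|---|---|---|---|---|
| 5% | 14.3% | 26.5% | 78.5% | 87.1% |
| 10% | 27.1% | 46.9% | 95.8% | 98.5% |
| 20% | 48.8% | 73.8% | 99.9% | over 99.9% |

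One missed subject moves a column by 100/n points: 100 at n = 1, 33.3 at n = 3, 16.7 at n = 6. In the overall column it is 3.3 points at N = 30 and 2.5 at N = 40.

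**6. Windows.** Section 12.6.1 chooses between values within a time window, while Section 12.3 applies none. As written, that rule has nothing to act on. If it did act, it would keep the nearest value, not the worst.

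**The case against.** The strongest reply is that little is lost in practice. Adverse event tables are not built on visits, so they are untouched. Listings keep every laboratory, ECG and ECOG value, and there are separate listings for liver tests of Grade 3 or higher and for possible Hy's law cases. All of that is true, and it limits the harm. It does not correct the counts and percentages in the tables.

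It is also fair that the plan does not show exclusion for every table. For Tables 3.14 and 3.15 the specific text points to all visits, so the fault there is a contradiction. Averaging planned ECG triplicates is conventional; the objection to averaging concerns repeat laboratory values at one time point. A re-test at another time point is not averaged by that rule. The SAP also does not say how often unscheduled draws are made for cause.

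Four stronger readings are tempting, but the document does not support them.

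- *The SAFE_L2 shell contradicts the rule.* It shows an unscheduled row and a worst-case row on the same day. But it is a listing shell, and Section 12.5.2 keeps unscheduled visits in listings.
- *The out-of-window sentence contradicts Section 12.3.* That sentence concerns protocol visit windows recorded as deviations; Section 12.3 can be read as analysis windows. Both can hold.
- *Best response in Table 2.1 omits unscheduled scans.* Section 8 defines confirmed, investigator-assessed best response without reference to visit scheduling. The omission would only be an inference from a general display rule.
- *Selection of the recommended Phase 2 dose was distorted.* Sections 3.1 and 3.1.1.1 base escalation on in-stream data, adverse event summaries and listings of serious events and dose-limiting toxicities, not on these final tables.

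**Conclusion.** The point holds for the reported safety tables. For Tables 3.8 and 3.9 the exclusion of unscheduled values is explicit. For Tables 3.14 and 3.15 the plan contradicts itself. For Tables 3.10, 3.11 and 3.13 the scope has to be stated. The most severe values can be missing; the document does not show that they are.

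The direction is certain: any bias is towards lower toxicity. The size is not. The 20% event rate and the 5–50% range of shares are assumptions, and the lower end is a modest loss (7.6 of 8 subjects shown). Averaging repeat laboratory values, and the mismatch between the window rule in Section 12.6.1 and Section 12.3, are smaller faults of the same kind.

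**What to change.** - State once, in Section 7 or Section 12.5.2, that every worst-case, maximum and any-post-baseline safety summary uses all on-treatment values: scheduled, unscheduled and out-of-window.
- Delete the word scheduled from the worst-case grade sentence in Section 7.3.
- Limit both exclusions in Section 12.5.2 to by-visit summaries.
- In Section 12.6.1, use the worst value for repeat safety laboratory tests and keep the mean for planned ECG triplicates.
- Reconcile Sections 7.3, 7.4, 12.3, 12.5.2 and 12.6.1, including whether any time window exists for the rule in Section 12.6.1.

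The cost is SAP wording and additional programming, mainly a flag for the values that enter worst-case derivations. Reported toxicity rates may become slightly less favourable. No new data are needed, since the listings already carry every value.

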12.5.3. Reporting Standards for Pharmacokinetic

Pharmacokinetic Concentration Data	
PC Windows Non-Linear (WNL) File	PC WNL file (CSV format) for the non compartmental analysis by Clinical Pharmacology Modelling and Simulation function will be created according to GUI_51487 : Non-compartmental Analysis of Pharmacokinetic Data. Note: Concentration values will be imputed as per GUI_51487
Descriptive Summary Statistics, Graphical Displays and Listings	Refer to IDSL PK Display Standards. Refer to IDSL Statistical Principle 6.06.1. Note: Concentration values will be imputed as per GUI_51487 for descriptive summary statistics/analysis and summarized graphical displays only.
Pharmacokinetic Parameter Data	
Is NQ impacted PK Parameters Rule Being Followed	Yes, refer to GUI_51487
Descriptive Summary Statistics, Graphical Displays and Listings	Refer to IDSL PK Display Standards. Refer to GUI_51487

12.6. Appendix 6: Derived and Transformed Data

12.6.1. General

Multiple Measurements at One Analysis Time Point

Mean of the measurements will be calculated and used in any derivation of summary statistics but if listed, all data will be presented.If there are two values within a time window the value closest to the target day for that window will be used. If values are the same distance from the target, then the mean will be taken.Participants having both High and Low values for Normal Ranges at any post-baseline visit for safety parameters will be counted in both the High and Low categories of “Any visit post-baseline” row of related summary tables. This will also be applicable to relevant Potential Clinical Importance (PCI) summary tables.
Study Day

Calculated as the number of days from First Dose Date:
Ref Date = Missing → Study Day = MissingRef Date < First Dose Date → Study Day = Ref Date – First Dose DateRef Date ≥ First Dose Date → Study Day = Ref Date – (First Dose Date) + 1

12.6.2. Study Population

Extent of Exposure

Number of days of exposure to study drug will be calculated based on the formula: Duration of Exposure in Days = Treatment Stop Date – (Treatment Start Date) + 1

12.7. Appendix 7: Reporting Standards for Missing Data

12.7.1. Premature Withdrawals

Element	Reporting Detail
General	
 A subject will be considered to have completed the study after they have completed their end of study visit or if the subject dies or is still in follow-up at the time the study is closed or terminated, whichever is sooner. Withdrawn subjects may be replaced in the study at the discretion of the Sponsor in consultation with the investigator. All available data from participants who were withdrawn from the study will be listed and all available planned data will be included in summary tables and figures, unless otherwise specified. Withdrawal visits will be summarised as withdrawal visits.

12.7.2. Handling of Missing Data

Element	Reporting Detail
General	
 Missing data occurs when any requested data is not provided, leading to blank fields on the collection instrument: 
 These data will be indicated by the use of a “blank” in subject listing displays. Unless all data for a specific visit are missing in which case the data is excluded from the table. Answers such as “Not applicable” and “Not evaluable” are not considered to be missing data and should be displayed as such.
Outliers	
 Any subjects excluded from the summaries and/or statistical analyses will be documented along with the reason for exclusion in the clinical study report.

12.7.2.1. Handling of Missing and Partial Dates

Imputed partial dates will not be used to derive study day, duration (e.g. duration of adverse events), or elapsed time variables.

With the exception of new anti-cancer start date on the Oncology time to event analysis dataset and exposure end date on the Exposure analysis dataset, imputed dates will not be stored on datasets.

Imputed dates will not be displayed in listings. However, where necessary, display macros may impute dates as temporary variables for the purpose of sorting data in listings only. In addition, partial dates may be imputed for ‘slotting’ data to study time periods or for specific analysis purposes as outlined below.

Element	Reporting Detail
General	
 Partial dates will be displayed as captured in subject listing displays.
Adverse Events	
 The eCRF allows for the possibility of partial dates (i.e., only month and year) to be recorded for AE start and end dates; that is, the day of the month may be missing. In such a case, the following conventions will be applied for calculating the time to onset and the duration of the event: 
 Missing Start Day: First of the month will be used unless this is before the start date of study treatment; in this case the study treatment start date will be used and hence the event is considered On-treatment as per Appendix 4: Study Phases and Treatment Emergent Adverse Events. Missing Stop Day: Last day of the month will be used, unless this is after the stop date of study treatment; in this case the study treatment stop date will be used. Completely missing start or end dates will remain missing, with no imputation applied. Consequently, time to onset and duration of such events will be missing.
Concomitant Medications/ Medical History	
 Partial dates for any concomitant medications recorded in the CRF will be imputed using the following convention: 
 If the partial date is a start date, a '01' will be used for the day and 'Jan' will be used for the month If the partial date is a stop date, a '28/29/30/31' will be used for the day (dependent on the month and year) and 'Dec' will be used for the month. 
The recorded partial date will be displayed in listings.

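### The SAP's partial-date rules for adverse events misdate some events at both ends of treatment, and the section contradicts itself on whether imputed dates feed AE duration

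*SAP*

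**What the plan says.** SAP Section 12.7.2.1 gives two conventions for AEs whose day of the month is missing.

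- **Start day missing:** "First of the month will be used unless this is before the start date of study treatment". If it is before, "in this case the study treatment start date will be used and hence the event is considered On-treatment".
- **Stop day missing:** "Last day of the month will be used, unless this is after the stop date of study treatment". If it is after, "in this case the study treatment stop date will be used".

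On the use of imputed dates, the section opens with a ban: "Imputed partial dates will not be used to derive study day, duration (e.g. duration of adverse events), or elapsed time variables". It then allows imputation to place data in study periods, "or for specific analysis purposes as outlined below". The AE row introduces its two conventions by saying that "the following conventions will be applied for calculating the time to onset and the duration of the event".

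Sections 12.4.1 and 12.4.2 set the window. AEs count from treatment start, Day 1 included, up to 30 days after treatment stop. An AE dated before treatment start belongs to the pre-treatment phase unless it worsens later.

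**The concern.** Moving a partial start to the first-dose date is a usual, cautious convention when the event may have begun on either side of first dose. That doubt exists only in the month of first dose. For an earlier month the recorded month and year already settle the matter, and the rule overrides them.

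The stop rule has the opposite fault. It takes the end of treatment as the latest possible end of an AE, although the SAP itself counts AEs that begin up to 30 days later. Neither rule checks that the stop falls on or after the start.

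The ban and the AE row would lead two programmers to derive different variables.

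AEs head the primary endpoint of Part 1 (Section 2.2) and are summarised by dose level (Section 7), and the dose levels begin with single subjects before the 3+3 stage (Section 2.3). Wherever the treatment-emergent flag is applied, one misplaced event could change a dose level from 0/1 to 1/1, or from 0/3 to 1/3.

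**Working it through.** The SAP gives no figure to reproduce here, so the rules were applied literally to test dates.

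**Inputs**
- Imputation rules: Section 12.7.2.1. Window: Section 12.4.2.
- Assumed for illustration: treatment start 20 April 2015, treatment stop 10 June 2015. The window therefore runs to 10 June + 30 days = 10 July.
- Assumed formula: duration = stop - start + 1. The SAP states this form only for exposure (Section 12.6.2); it is carried over to AEs by analogy.

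**Rules as written**

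| Recorded AE dates | Dates after imputation | Treatment-emergent? | Duration (days) |
|---|---|---|---|
| Feb to Mar, both days missing | 20 Apr to 31 Mar | yes | -20 + 1 = -19 |
| Feb (day missing) to 15 Mar | 20 Apr to 15 Mar | yes | -36 + 1 = -35 |
| Apr to May, both days missing | 20 Apr to 31 May | yes | 41 + 1 = 42 |
| 25 Jun to Jul (day missing) | 25 Jun to 10 Jun | yes | -15 + 1 = -14 |
| Jul to Jul, both days missing | 1 Jul to 10 Jun | yes | -21 + 1 = -20 |
| 1 Jun to Jul (day missing) | 1 Jun to 10 Jun | yes | 9 + 1 = 10, against up to 61 to 31 Jul |

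Rows 1 and 2 are wholly pre-treatment events turned into Day 1 events. Row 3 lies in the first-dose month and is handled acceptably. Rows 4 and 5 start inside the follow-up window and end before they start. Row 6 is cut short.

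**General result for the stop rule.** Suppose an AE starts k days after treatment stop, with k from 1 to 30, and its stop day is missing. The last day of its stop month is on or after its onset, hence after treatment stop, so the cap always applies. Duration = -k + 1, which runs from 0 (k = 1) to -29 (k = 30). All 30 onset days give an impossible value.

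**Which faults depend on the contradiction.** Moving the start alters the treatment-emergent flag on either reading, because placing events in study periods is expressly allowed and the rule itself declares the event on-treatment. The impossible and shortened durations arise only if the AE row prevails over the opening ban. If the ban prevails, no duration is derived from imputed dates, and the AE row's stated purpose is empty.

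**Same cases under the corrected rules.** Row 1: 1 Feb to 31 Mar, not treatment-emergent, 59 days. Row 2: 1 Feb to 15 Mar, not treatment-emergent, 43 days. Row 3: unchanged at 42 days. Row 4: 37 days. Row 5: 31 days. Row 6: 61 days. No negative value remains.

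**Why a same-month condition alone is not enough.** An AE with start April (day missing) and known stop 10 April matches the first-dose month. Moving its start to 20 April gives 10 - 20 + 1 = -9 days and a treatment-emergent flag. A further guard is needed: do not move the start if the AE is known to have ended before first dose.

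**The case against.** The strongest reply concerns consequences. A reader might infer that the primary safety counts are inflated. The SAP does not support that. AE Tables 3.1 to 3.7 (Section 12.10.7) cover all, common non-serious, treatment-related or serious events; none is titled treatment-emergent, and Section 7.2 states no such restriction. A February event would appear among all AEs however it is classified. Section 7.2 does defer to sponsor data standards that are not shown, so use of the flag cannot be excluded, but it is not demonstrated. This objection stands.

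Appendix 10 also lists no summary of AE onset or duration. Section 12.7.2.1 keeps imputed AE dates out of stored datasets and listings. Negative durations therefore have no named output, and they arise on only one of two readings. This too stands, and it limits the size of the point.

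The allowance for specific analysis purposes might be offered as reconciling the ban with the AE row. It does not: the ban names AE duration as its own example, and the AE row uses imputed dates for exactly that.

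A further inference concerns the note in Section 12.4.2: "If the study treatment stop date is missing, then the AE will be considered to be On-Treatment". Read alone, it could seem to make every AE on-treatment whatever its onset. It sits under a two-sided window, however, and its natural role is to waive the upper limit when that limit cannot be computed. It is not treated here as an error.

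Finally, only AEs with a missing day are affected, in a terminated study with descriptive analyses and an abbreviated report. How often an AE record carries a start month before treatment depends on collection rules that the SAP does not give.

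**Conclusion.** The rules are wrong as written in three respects: the start rule lacks a same-month condition, the stop rule's cap ignores the 30-day window, and the section gives opposite instructions on AE duration. The first conflicts with the SAP's own phase and treatment-emergent definitions and affects the flag on any reading. The second yields impossible or shortened durations if the AE row prevails.

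The effect is confined to AEs with a missing day, and reaches the treatment-emergent flag and any derived onset or duration. Their number is unknown, and no planned table is shown to change. The numerical examples rest on assumed treatment dates and an assumed duration formula; the direction of each fault does not depend on the particular dates. This merits correction before programming but does not threaten the trial's main conclusions.

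**What to change.** In Section 12.7.2.1:

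1. **Start day missing:** use the first-dose date only if the recorded month and year equal those of first dose and the AE is not known to have ended before first dose. Otherwise use the first of the recorded month.
2. **Stop day missing:** use the last day of the recorded month, without a cap at treatment stop, and never earlier than the AE start.
3. **Use of imputed dates:** keep one statement on whether they feed AE onset and duration, and make the opening paragraph and the AE row agree with it.

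Optionally, add to the note in Section 12.4.2 that a missing treatment stop date waives only the upper limit, so that onset or worsening must still be on or after treatment start.

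The cost is a few lines of SAP text and a small change to the date-imputation program. No new data are needed.
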